#### STUDY 2:

Participants act as their own controls and before/after differences are analyzed with or univariate ANOVA for repeated measurements.

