## STUDY 2:

The etiology of shortness of breath is multifactorial, and shortness of breath can be a symptom of a wide range of lung or heart diseases. In failing heart pump function, shortness of breath is one of the most frequent symptoms. Heart failure can be treated with various types of medicine, but in severe heart failure so that sufficient circulation cannot be maintained, heart transplantation may be the only treatment. Shortage of transplant organs results in waiting time for transplantation. Therefore, an LVAD has been developed that can maintain adequate blood circulation as either temporary treatment before heart transplantation or as definitive treatment in patients who cannot undergo regular heart transplantation. The LVAD is implanted in the thorax and helps pump blood from the left ventricle into the aorta. The LVAD is located on top of the left hemidiaphragm and can therefore inhibit the movement of the diaphragm. Thereby, the LVAD can give rise to shortness of breath, and in patients who have concurrent heart failure, it can thus be difficult to assess whether shortness of breath is due to heart failure or reduced diaphragm function. Treatment that these conditions are different.

Heart transplantation entails a complete replacement of the heart. Due to the close relationship with the phrenic nerve, this can be damaged during the operation and thus result in reduced diaphragm function.

Some diseases, e.g. Cancer of the lung, mediastinum and esophagus requires thoracic surgery. Nerves to the diaphragm can be damaged during the operation and thereby cause reduced diaphragm function, which can lead to shortness of breath. Pleural effusion is common after thoracic surgery and also manifests as shortness of breath. In addition, patients often have other competing diseases such as chronic obstructive pulmonary

disease (COPD) or heart failure, which can also cause shortness of breath. This results in complex diagnostic conditions and complicates the investigation of shortness of breath after thoracic surgery.

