## HYPOTHESIS/AIM

- 1. To compare the precision of different ultrasound examination methods for assessing diaphragm function compared with X-ray translucency.
- 2. Investigate whether LVAD implantation, heart transplantation and thoracic surgery affect diaphragm function.

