## STUDY 2:

In study 2, only lung function examination and ultrasound examination are carried out. These are made

Lung cancer: 1) the day before surgery, 2) 3 days after surgery and 3) 2 weeks after surgery.

Oesophageal cancer: 1) the day before surgery, 2) 3 days after surgery and 3) 10 days after surgery (after which most are discharged).

LVAD implantation: 1) the day before surgery, 2) 14 days after surgery and 3) 3 months after surgery.

Heart transplant: 1) in close relation to the write-up on the heart transplant list, 2) 14 days after the operation and 3) 3 months after the operation

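### Study 2's one-sentence analysis does not say how missed visits are handled and has no surgery-type term; a mixed model using all visits would settle both at little cost

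*Combined protocol and SAP*

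**What the plan says.** The Data analysis section gives Study 2 a single sentence: "Participants act as their own controls and before/after differences are analyzed with or univariate ANOVA for repeated measurements". A first method appears to have been lost before 'or'. Neither this section nor any other gives a rule for a patient who misses a scan, a factor for type of surgery, or separate analyses by operation.

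Other sections bear on both points:

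- **Aim** (Hypothesis/aim): "Investigate whether LVAD implantation, heart transplantation and thoracic surgery affect diaphragm function". The layman's summary (Background & purpose) lists four types of surgery and asks how far each affects the diaphragm.
- **Mechanism** (Background, Study 2). For the device: "The LVAD is located on top of the left hemidiaphragm and can therefore inhibit the movement of the diaphragm". For transplantation: "Due to the close relationship with the phrenic nerve, this can be damaged during the operation and thus result in reduced diaphragm function".
- **Schedule** (Surveys, Study 2): "Lung cancer: 1) the day before surgery, 2) 3 days after surgery and 3) 2 weeks after surgery"; the oesophageal third visit is at 10 days. "LVAD implantation: 1) the day before surgery, 2) 14 days after surgery and 3) 3 months after surgery". The transplant baseline differs: "Heart transplant: 1) in close relation to the write-up on the heart transplant list".
- **Sample size** (Strength calculation, Study 2): 36 lung/oesophageal patients, raised to 50 partly for drop-outs, and about 40 LVAD/transplant patients with no power calculation. Drop-outs enter only as a reason to recruit more.

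**The concern.** Two choices that affect the primary result are left open.

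**Incomplete patients.** A univariate repeated-measures ANOVA can be run on patients with all three visits, which is the usual form. It can also be run in long format with patient and visit effects, which keeps everyone. A paired comparison at each visit is a third possibility. These give different answers if the patients who miss the last scan are those whose diaphragm moved least, or most, after surgery. If the choice is not fixed beforehand, it can be made after the data are seen.

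**Effect per operation.** The aim names LVAD implantation and heart transplantation separately, the background gives them different mechanisms, and their baselines are taken at different points. If the two were averaged, the result would be the effect of neither. The plan does not say whether they are.

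**Working it through.** **1. The plan's own figure.** Inputs from Strength calculation, Study 2: mean 6.65, SD 2.38, 20% change, power 0.9, alpha 0.05. The change is 0.20 × 6.65 = 1.33. In a two-sided paired t-test with 2.38 as the SD of the before-after difference, the standardised change is 1.33/2.38 = 0.559 and n = 36 gives power 0.903. The stated 36 reproduces, as a single before-after contrast in the pooled lung/oesophageal group. If 2.38 is the SD at one visit, this amounts to a correlation of 0.5 between visits, since 2.38 × √(2 × (1 − 0.5)) = 2.38.

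**2. Patients lost in a complete-case analysis.** The documents give no missing-visit rate, so a range is assumed. If each of two post-operative visits is missed independently with probability m, complete cases are N(1 − m)².

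| m | of 50 | of 40 |
|---|---|---|
| 10% | 40.5 | 32.4 |
| 15% | 36.1 | 28.9 |
| 20% | 32.0 | 25.6 |

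The margin from 36 to 50 is used up at about 15% per visit. When missingness is unrelated to change, nothing is biased. At 10-20% per visit the complete-case standard error is then about 7-16% larger than with all visits (r = 0.5).

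**3. Possible shift in the estimate.** Simulation with mean 6.65, SD 2.38 at each visit, and a true fall of 1.33 (20%) at both post-operative visits. The third visit is missing with log-odds linear in the standardised early fall. Results are for 10% and then 20% missing.

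| Assumption | Method | First post-op visit | Second post-op visit |
|---|---|---|---|
| slope 1, all r = 0.5 | complete-case | 16.8, 13.8% | 18.4, 16.9% |
| same | long-format ANOVA | 20.0, 20.0% | 20.0, 20.0% |
| same | mixed model | 20.0, 20.0% | 20.0, 20.0% |
| slope −0.5, all r = 0.5 | complete-case | 21.8, 23.5% | 20.9, 21.8% |
| slope 0 | any | about 20% | about 20% |
| slope 1; r = 0.5 with baseline, 0.8 between post-op scans | complete-case | 16.8, 13.8% | 17.4, 15.1% |
| same | long-format ANOVA | 20.0, 20.0% | 19.0, 18.2% |
| same | unstructured mixed model | 20.0, 20.0% | 20.0, 20.0% |

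In the first row the second-visit bias is half that at the first. With all correlations 0.5, the covariance of the two falls is (1 − 0.5 − 0.5 + 0.5) = 0.5 of the variance of one fall. The shortfall of 6.2 points (20 − 13.8) therefore becomes 3.1.

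A paired difference at the first visit uses every patient scanned there, so it stays at 20% in all these scenarios.

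**4. Precision per operation.** The 95% half-width as a share of baseline is t × 2.38/√n/6.65. The split between operations is assumed.

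| n | Half-width (points) | Power for a 20% change |
|---|---|---|
| 25 | 2.064 × 2.38/5/6.65 = 14.8 | 76% |
| 20 | 2.093 × 2.38/4.472/6.65 = 16.7 | 66% |
| 10 | 2.262 × 2.38/3.162/6.65 = 25.6 | 35% |

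**The case against.** The strongest reply is that the size of the bias is assumption throughout. The missing rate, the slope and the correlations are not in the documents. Slope 1 means that the odds of missing the scan multiply by 2.7 per SD of early fall, and the direction depends on a sign nobody knows. Ethical considerations (Study 2) places scans at visits already planned, and most oesophageal patients are still in hospital at day 10, so few scans may be missed. The sentence speaks of before/after differences. Read as a paired comparison at each visit, it leaves the first post-operative result unbiased. A long-format ANOVA, which the wording allows, is also unbiased in the main scenario. All of this stands, and it limits the point to an improvement.

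Three stronger readings are tempting, and the documents do not support them:

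- **That the planned analysis is biased.** It is not specified closely enough to say so.
- **That it wrongly assumes sphericity.** The missing words could name a multivariate method, which makes no such assumption; the Study 1 analysis uses MANOVA. No fault can be charged to lost text.
- **That the plan averages operations that should be kept apart.** No passage says that it averages. For lung and oesophageal surgery the aim speaks of thoracic surgery as one category, and the sample size treats the pair as one group. Only the layman's summary separates them. The case for separate results is firm for LVAD and transplant, and weaker for the cancer pair.

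It is also fair that a model reporting every operation at every visit would drop the pooled contrast for which 36 was calculated and leave no primary comparison. The fix has to prevent that.

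**Conclusion.** The point holds as an inexpensive improvement. The legible Study 2 method gives no missed-visit rule and no surgery-type term, although drop-outs are expected and the aim names LVAD and transplant separately. Whatever stood before 'or', a method name such as a paired test or multivariate ANOVA would supply neither.

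The potential shift is about 3-6 points of a true 20% fall at the first post-operative visit and 2-3 points at the second. This applies if patients are analysed complete-case, 10-20% of third visits are missing, missingness depends strongly on the early fall, and all correlations are 0.5. It is zero if missingness is unrelated to change, and it reverses with the opposite dependence. The gain of an unstructured mixed model over a long-format ANOVA is smaller, at most 1.8 points in the fall-related scenarios tabulated, against per-operation half-widths of 15 to 26 points. The main benefit is therefore a rule fixed in advance and an answer for each operation that the aim names.

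**What to change.** Replace the Study 2 analysis sentence with wording such as this:

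*Change in M-mode movement is analysed with a linear mixed model using all recorded visits, fitted separately for lung/oesophageal and for LVAD/transplant patients. The model contains categorical visit, surgery type, their interaction and an unstructured within-participant covariance, common to both types unless numbers allow separate matrices (REML, Kenward-Roger degrees of freedom). For lung/oesophageal patients the primary contrast is the pooled change from baseline at one post-operative visit named beforehand; change per operation is secondary. For LVAD and transplant, change is reported per operation. Changes per operation are estimates with 95% confidence intervals.*

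When naming the primary visit, note that day 3 is common to both cancer operations, whereas the third visit falls at 2 weeks or 10 days. Make no power claim per operation. Report, for each operation, the number measured at each visit and the reasons for missed visits, with deaths counted separately.

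If the ANOVA is kept, the least that is needed is to state that patients with a missed visit are retained, and for which operations results are given separately.

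The cost is wording and standard software, with no extra patients or visits. Three limits remain:

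- Estimates per operation are imprecise.
- The model only partly corrects the case where the early scan itself is missing because of the fall (17.8-15.7% for a true 20%, at 10-20% missing, slope 1, r = 0.5).
- The model does not remove the interval between listing and surgery from the transplant baseline.

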#### BLINDING

Analysis of ultrasound films is performed blinded to data for translucency in study 1.

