## ULTRASOUND EXAMINATIONS:

The participants are examined in a standing/sitting position with ultrasound in the mid-axillary line with the liver/spleen as a reference point on the right and left side. A movie clip is saved for later analysis.

Diaphragm movement is measured in 3 different ways: M-mode, Area method and B-mode. [1] [2] [3] [4] Diaphragm thickening fraction is measured in 1 way. [5]

Normal and deep breathing is carried out.

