#### TRANSLUCENT:

Performed only in study 1. Film clips of the movement of the diaphragm during X-ray translucency are recorded.

Transillumination, inspiratory pressure measurement and ultrasound examination are carried out simultaneously. Normal and deep breathing is carried out.

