## ENDPOINTS

#### STUDY 1:

Diaphragm movement and thickening fraction compared to the cranial movement of the diaphragm as measured by translucency (gold standard) for the following measures:

Primary endpoint:

• Movement of the right hemidiaphragm: 1. M-mode method.

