## Primary endpoint

o M-mode method of diaphragm movement (ultrasound, only on the right hemidiaphragm).

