## DATA ANALYSIS

#### STUDY 1:

Movement is measured continuously (centimeters or square centimeters) and calculated as a mean with standard deviation for the various ultrasound measurements. Correlation between diaphragm movement and sex, age, BMI is analyzed with multivariable analysis of variance, MANOVA.

The different measurement methods are compared individually with the golden standard with the paired T-test (Wilcocon's test if non-parametric). The 0 hypothesis is that there is no difference between the index method and the golden standard. Data is also depicted with a Bland-Altman plot and correlation between the index test and the golden standard.

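### Blinding covers only the ultrasound reading in Study 1; Study 2 clips may be read knowing the time point and Study 1 fluoroscopy knowing the ultrasound result, which can bias both primary endpoints

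*Combined protocol and SAP*

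**What the plan says.** The Blinding section is one sentence: "Analysis of ultrasound films is performed blinded to data for translucency in study 1". The layman's summary adds nothing to it.

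Both kinds of image are stored. For ultrasound, in both studies, "A movie clip is saved for later analysis" (Ultrasound examinations). For fluoroscopy, in Study 1 only, "Film clips of the movement of the diaphragm during X-ray translucency are recorded" (Translucent). In Study 1 the two are acquired together: "Transillumination, inspiratory pressure measurement and ultrasound examination are carried out simultaneously".

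Both primary endpoints are read from these clips. In Study 1 the endpoint is "Movement of the right hemidiaphragm: 1. M-mode method", set against fluoroscopy as the reference. Data analysis tests it with a paired test: "The 0 hypothesis is that there is no difference between the index method and the golden standard". In Study 2 it is change over time in "M-mode method of diaphragm movement (ultrasound, only on the right hemidiaphragm". There is no comparison group: "Participants act as their own controls".

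No section gives the number of readers, whether different people read the two methods, how clips are coded, or the reading order.

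**The concern.** Measuring excursion on a saved clip takes judgement, for example in choosing the breath and placing the markers. A reader who knows what the answer is likely to be can lean towards it without intending to.

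In Study 2 the exposed knowledge is the time point. The Background gives reasons to expect less movement after surgery (phrenic nerve injury, an LVAD resting on the left hemidiaphragm). With no control arm, a small lean in the post-operative readings cannot be told apart from an effect of surgery, and no later analysis can remove it.

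In Study 1 the exposed reading is the reference. If fluoroscopy is measured by someone who knows the ultrasound value, the reference can drift towards the index method. The differences then shrink and agreement looks better than it is. The Ethical considerations section says that good agreement would make fluoroscopy unnecessary in future, so an error in this direction would matter.

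**Working it through.** **1. What is masked**

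| Reading | Masked to | Stated in the plan? |
|---|---|---|
| Study 1 ultrasound | fluoroscopy values | yes |
| Study 1 fluoroscopy | ultrasound values | no |
| Study 1, either method | disease group | no |
| Study 2 ultrasound | time point, surgery type | no |

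**2. Inputs for Study 2 (Strength calculation, lung/oesophageal cancer patients)**

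Mean 6.65 mm, SD 2.38 mm, clinically relevant change 20% (0.20 × 6.65 = 1.33 mm), power 0.9, alpha 0.05, 36 patients needed, 50 to be included. Sidedness is not stated; I take it as two-sided.

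**3. Reproducing the plan's figure**

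Paired t-test with 2.38 as the SD of change. The noncentrality is δ = (change / SD) × √n. At n=36, δ = (1.33 / 2.38) × 6 = 3.35, and the noncentral t distribution with 35 df gives power 0.903. The smallest n reaching 0.9 is 36, as the plan states. The plan has therefore in effect used 2.38 as the SD of the before/after change, and I keep that value.

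**4. False-positive rate if post-operative readings are shifted**

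Set the true change to zero and add a systematic shift b to the post-operative readings. The rejection probability comes from the same formula with δ = (b / 2.38) × √n. The values of b are assumptions; the documents give none.

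| Assumed shift | b (mm) | δ at n=36 | Rejects, n=36 | δ at n=50 | Rejects, n=50 |
|---|---|---|---|---|---|
| 2% | 0.133 | 0.34 | 6.2% | 0.40 | 6.7% |
| 5% | 0.333 | 0.84 | 12.9% | 0.99 | 16.2% |
| 10% | 0.665 | 1.68 | 37% | 1.98 | 49% |

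The nominal rate is 5%. A fixed shift does more harm as n grows, so enrolling 50 instead of 36 does not protect against it.

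**5. Sensitivity to the SD of change**

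The plan reports 2.38 as the SD of movement. If that is the SD at each visit and r is the pre/post correlation, SD of change = 2.38 × √(2(1 − r)). Using 2.38 itself implies r = 0.5. For a 5% shift at n=36:

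- r = 0.2: SD 3.01, rejects 9.9%
- r = 0.5: SD 2.38, rejects 12.9%
- r = 0.8: SD 1.51, rejects 25%

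**6. Sensitivity to the test**

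The plan names repeated-measures ANOVA. With three visits, both post-operative visits shifted by 5%, sphericity and n=36, the noncentrality is 36 × (2/3) × 0.3325² / (2.38² / 2) = 0.94. The F test on 2 and 70 df then rejects 12.4% of the time, close to the 12.9% above.

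**7. Study 1, illustration**

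Take n=100, a true bias of 10%, and the plan's SD of 36% as the SD of differences.

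- If drift of the reference halves the mean bias to 5% and leaves the SD unchanged, δ falls from (10/36) × 10 = 2.78 to 1.39, and power to detect the bias falls from 79% to 28%.
- If drift halves every difference, the test's power is unchanged, but the half-width of the limits of agreement falls from 1.96 × 36 = 71% to 1.96 × 18 = 35%.

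Halving is an assumption chosen to show the mechanism.

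**The case against.** A reader might infer from the Blinding section that Study 2 clips will be read by someone who knows the time point, that Study 1 fluoroscopy will be read with the ultrasound value in hand, and that both primary endpoints are therefore biased. The documents do not support that. They do not say who reads the clips, in what order or with what information. Silence supports "may" and "can", no more.

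Study 1 is also partly protected. The index reading, which supplies the primary measure, is already masked; only the reference reading is open.

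The direction in Study 2 is not settled either. The Background gives reasons for a fall, but the stated aim is neutral, the sample size targets a change of either sign, and the layman's summary calls it unclear whether surgery has lasting or short-term effects. A post-operative fall is the plausible direction for a lean.

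The percentages are illustrations. At a 2% shift the inflation is slight, the 5% figure moves from 9.9% to 25% with the pre/post correlation, and the figures cover only the lung/oesophageal cohort, not the LVAD/transplant patients.

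Masking also has limits. An LVAD may be visible on the film, and the Background notes that effusion is common after thoracic surgery, so a clip can reveal its own group or time point. Masked reading does nothing about an examiner who knows the visit while acquiring the image.

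All of this stands, and it limits the claim. It does not remove the gap: one direction in one study is masked, and the remaining readings feed both primary endpoints.

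**Conclusion.** The concern holds as a preventable risk, not as a demonstrated bias. Following the plan as written leaves two things open to reader expectation: the Study 2 primary endpoint and the reference side of the Study 1 primary comparison. Study 2 is the more serious because nothing in its design can separate a reading shift from an effect of surgery.

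The size depends on a shift that the documents do not give. Over assumed shifts of 2% to 10%, the nominal 5% error rate becomes 6.2% to 37% at n=36, or 6.7% to 49% at n=50. This assumes a two-sided test, no true change and 2.38 mm as the SD of change. The largest of these shifts is half the 20% change that the plan regards as clinically relevant. The omission itself is certain from the text. Masking should be specified before the clips are read.

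**What to change.** Replace the Blinding section with text such as:

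> Study 1: ultrasound and fluoroscopy clips are each coded, stripped of identity and read in separate random order, blinded to the other method's values and, where possible, to disease group. If one person reads both, the modalities are read in separate sessions under different codes.
>
> Study 2: all clips are stripped of date, visit and identity, coded, and read in random order after the patient's last visit.

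The cost is one protocol paragraph and the work of coding clips that are stored anyway. It adds no visits, procedures, radiation or patients. Study 2 reading becomes batched, so results are not available visit by visit.

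The protocol should also state what the change does not achieve: masking may be incomplete where a device or effusion can be seen, and bias at image acquisition remains.

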## **RISKS AND DISADVANTAGES**

## STUDY 1 & 2:

Ultrasound examination, lung function examination and manometry are without risks.

